13.0 CRITERIA FOR REMOVAL FROM STUDY

- Disease progression. *However*, patients with evidence of clinical disease progression or radiographic progression (such as on the 1-124 PET/CTs or other scans) before the 6-month evaluation following vemurafenib, copanlisib, and 1-131 may continue on the protocol to complete all mandated assessments if the treating physician deems it clinically reasonable. If there is evidence of disease progression before completing treatment with vemurafenib and copanlisib, study treatment with these drugs and 1-131 will be allowed to continue if the treating physician deems that such a decision is clinically justifiable.
- Initiation of new drug treatment for thyroid cancer.
- Death
- Decision of patient to withdraw from the study.
- Completion of all planned study therapies and assessments.

We will determine the proportion of patients with *BRAF* mutant RAI^r thyroid cancer in which the combination of vemurafenib and copanlisib administered at the MTD increases iodine incorporation in thyroid cancer metastases such that a dose of 2000 cGy can be delivered to at least 1 tumor with 5300 mCi of 1-131. Once the MTD is identified, up to an additional 4 patients will be enrolled in the cohort, to bring the total number of patients treated at the MTD to 10. As an added precaution for safety, if 2 of the additional 4 patients experience a DLT, further accrual will be halted; the next dose 1 level below will be evaluated for DLT in a minimum of 6 patients, and expanded to include 10 total if 1 experience DLT. The proportion of patients treated at all vemurafenib and copanlisib dose levels who experienced increased iodine incorporation sufficient to warrant 1-131 treatment will also be calculated. The number of patients with sufficiently increased RAI uptake to warrant treatment with 1-131 will be analyzed using proportions and corresponding confidence intervals.

We will also determine the ORR (per RECIST v1.1) and the proportion of patients who are alive without disease progression (per RECIST v1.1) at the 6-month time point (this refers to the assessments designated to occur ~6 months after 1-131 therapy) for patients who receive 1-131 therapy. Patients who have completed the second 1-124 PET/CT and received 1-131 therapy, but did not complete the 6-month evaluation, will be considered to have had a progression/death event for the PFS analysis and will be categorized as nonresponders for the ORR analysis. The ORR will be analyzed using proportions and corresponding confidence intervals.

It is possible that patients will have clinical or RECIST v1.1 radiologic evidence of disease progression before the 6-month evaluation for several reasons: (1) vemurafenib and copanlisib, without the addition of 1-131, may not have significant clinical efficacy; (2) Thyrogen stimulation can transiently increase tumor size, which can be mistaken for disease progression; (3) the therapeutic effects of 1-131 can be delayed; and (4) evidence of progression may be present before administration of 1-131. Hence, patients with evidence of disease progression after 1-131, but prior to the 6-month evaluation, may remain on the study to complete the 6-month assessments if the treating physician deems that such a decision is clinically justifiable. If there is evidence of disease progression before completing treatment with vemurafenib and copanlisib, study treatment with these drugs and 1-131 will be allowed to continue if the treating physician deems that such a decision is clinically justifiable. The final objective response and disease progression assessments at 6 months for these patients will be based on a comparison between the 6-month radiologic scan(s) and the baseline, prestudy radiologic scans. However, if in the opinion of the treating physician, patients with evidence of progression before the 6-month assessment are unlikely to experience benefit by the 6-month time point, the patients will be considered to have had a

progression/death event for the PFS analysis, categorized as nonresponders for the ORR analysis, and removed from the study.

Patients who receive additional treatment for thyroid cancer outside of this protocol before the 6-month time point (except for TSH suppression, palliative radiation to a nontarget lesion, or therapy to prevent pathologic fractures caused by bone metastases [e.g., zoledronic acid and denosumab]) will be considered to have had a progression/death event for the PFS analysis and will be categorized as nonresponders for the ORR analysis.

To characterize how the combination of vemurafenib plus copanlisib affects RAI uptake and retention within select index lesions, we propose to analyze the 4 PET/CT scans obtained in each the pretreatment and on-treatment periods. This analysis will directly test our hypothesis that the combination of vemurafenib plus copanlisib affects not only RAI uptake but also retention within thyroid tumors. These data will be analyzed using descriptive statistics.

Exploratory Objectives:

We will perform correlative studies on serial research biopsy specimens and archival tumor tissue in order to evaluate the effect of vemurafenib on (1) expression and phosphorylation of 1VIAPK signaling pathway proteins; (2) expression and phosphorylation of negative feedback loops connected to the 1VIAPK pathway (such as HER3); (3) quantitative levels of mRNA transcripts for 1VIAPK, PI3K, and S1\IAD signaling pathways, as well as thyroid-specific gene products; and (4) the presence of other genetic alterations (through the use of MSK-IMPACT, supplemented, if needed, by the RNA Targeted Archer Solid Tumorfusion panel). These analyses will be descriptive and exploratory, given the limited number of samples examined. Changes in these molecular profiles will be correlated directly with the changes in RAI uptake and retention measured on the 1-124 PET/CT scans. These data will be analyzed using descriptive statistics.

Another exploratory objective will be to evaluate time to next thyroid cancer treatment, tumor size changes after study therapy, serum thyroglobulin changes and survival. This data will be important for gaining more insight into the degree of tumor control that may be achieved with vemurafenib plus copanlisib +/- 1-131. To collect this data beyond the protocol-mandated scans and tests, an observation period to collect data for up to 1 year after study drug discontinuation will be completed for all patients. Data that to be collected will include RECIST measurements of both protocol-mandated scans and scans conducted as part of standard of care. Thyroglobulin/TSH serum values draw on protocol and as part of standard of care will also be collected. Other data to be collected are survival status and initiation of new treatments (radiation, surgery and drug therapy). If RECST disease progression and initiation of drug therapy, or death, is observed, the observation phase may be discontinued. Data encompassing this observation phase may also be collected/analyzed retrospectively. This exploratory analysis will be conducted using descriptive statistics.

Sample size: 6-32 patients. We plan to accrue about 1-2 patient(s) per month for a total accrual time of 1-2 years.

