Non-measurable disease: All other lesions (or sites of disease), including small lesions (longest diameter <10 mm or pathological lymph nodes with 2:10 to <15 mm short axis), are considered non-measurable disease. Bone lesions, leptomeningeal disease, ascites, pleural/pericardial effusions, lymphangitis cutis/pulmonitis, inflammatory breast disease, and abdominal masses (not followed by CT or MRI), are considered as non-measurable.

Note: Cystic lesions that meet the criteria for radiographically defined simple cysts should not be considered as malignant lesions (neither measurable nor non-measurable) since they are, by definition, simple cysts.

'Cystic lesions' thought to represent cystic metastases can be considered as measurable lesions, if they meet the definition of measurability described above. However, if non-cystic lesions are present in the same patient, these are preferred for selection as target lesions.

Target lesions: All measurable lesions up to a maximum of 2 lesions per organ and 5 lesions in total, representative of all involved organs, should be identified as **target lesions** and recorded and measured at baseline. Target lesions should be selected on the basis of their size (lesions with the longest diameter), be representative of all involved organs, but in addition should be those that lend themselves to reproducible repeated measurements. It may be the case that, on occasion, the largest lesion does not lend itself to reproducible measurement in which circumstance the next largest lesion which can be measured reproducibly should be selected. A sum of the diameters (longest for non-nodal lesions, short axis for nodal lesions) for all target lesions will be calculated and reported as the baseline sum diameters. If lymph nodes are to be included in the sum, then only the short axis is added into the sum. The baseline sum diameters will be used as reference to further characterize any objective tumor regression in the measurable dimension of the disease.

Non-target lesions: All other lesions (or sites of disease) including any measurable lesions over and above the 5 target lesions should be identified as **non-target lesions** and should also be recorded at baseline. Measurements of these lesions are not required, but the presence, absence, or in rare cases unequivocal progression of each should be noted throughout follow-up.

Methods for Evaluation of Measurable Disease

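### The 6-month event rule exempts palliative radiation to a nontarget lesion even when nontarget progression was already documented, so a progressed patient can be scored progression-free

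*Combined protocol and SAP*

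**What the plan says.** **Additional-treatment rule (Section 14, secondary objectives).** "Patients who receive additional treatment for thyroid cancer outside of this protocol before the 6-month time point" are scored as a progression/death event for PFS and as nonresponders for ORR, "except for TSH suppression, palliative radiation to a nontarget lesion, or therapy to prevent pathologic fractures caused by bone metastases". The radiation exemption depends only on the lesion being nontarget. Neither the reason for the radiation nor the lesion's earlier status matters.

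**Early progression (Section 14).** The plan allows that "patients with evidence of disease progression after 1-131, but prior to the 6-month evaluation, may remain on the study to complete the 6-month assessments", subject to the treating physician's judgment. Their final response and progression status is then "based on a comparison between the 6-month radiologic scan(s) and the baseline, prestudy radiologic scans". The exception is a judgment by the treating physician that "patients with evidence of progression before the 6-month assessment are unlikely to experience benefit by the 6-month time point"; the patient then counts as an event and a nonresponder.

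**Progression and PFS (Section 12).** Nontarget disease includes measurable lesions beyond the five targets and non-measurable sites ("Bone lesions, leptomeningeal disease, ascites, pleural/pericardial effusions" among them). Unequivocal nontarget progression is PD, but it must reflect a change in the disease overall, and growth of one lesion is normally not enough. PFS runs from the start of vemurafenib to the first progression or death.

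**Purpose (Section 2.0).** The 6-month ORR and PFS are meant to show whether the drug combination enhances I-131 activity.

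**The concern.** Section 14 gives reasons for not treating early progression as final: Thyrogen can enlarge tumors transiently, and I-131 may act late. Both suppose that later shrinkage of the lesion tells us something about I-131. Once the lesion has had external-beam radiation, its later shrinkage can no longer be attributed to I-131.

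The exemption is reasonable for radiation given for symptoms when progression has not been documented. Where nontarget PD is already on record, the same wording allows an effect of external radiation to enter a 6-month result that will be read as I-131 activity. The error runs in one direction, towards a more favourable rate. The denominator is small, and Section 3.4 intends the 10-patient vemurafenib pilot as a comparator for judging what copanlisib adds, so single patients matter.

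**Working it through.** The available text gives no power, precision or event-rate figure for 6-month PFS or ORR, so there is no plan figure to reproduce. The check has two parts: whether the rules permit the outcome, and how much one patient counts.

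**1. Do the rules permit it?**

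- *Time window.* Section 9.5 and Table 9-2 bar radiotherapy while on study medication. The exemption therefore operates mainly from the end of drug treatment (about 2 days after I-131) to 6 months.
- *Progression is documented.* Table 10-3 schedules imaging at 3-4 months after I-131. Suppose nontarget PD meeting the full Section 12 standard is recorded there.
- *The patient stays on study.* Section 14 allows this. Section 13 lists new drug treatment as a reason for removal, but not radiation.
- *Radiation is given to a nontarget lesion.* Under the exemption this is not an event.
- *6-month reading.* The scan is compared with baseline. If the irradiated lesion has regressed so that nontarget disease no longer reads as unequivocal progression against baseline, and nothing else has progressed, the patient is scored progression-free.
- *Response.* If the target lesions have also fallen by at least 30%, the Section 12 response table gives PR, because the nontarget PD that would have overridden it is gone.
- *Remaining check.* Only the physician's judgment that benefit is unlikely turns this patient into an event.

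Under Section 12's definition of PFS to first progression, the same patient had an event at 3-4 months. The two sections give different answers for one patient. No available section excludes an irradiated lesion from the 6-month reading or plans a sensitivity analysis.

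**2. How much does one patient count?**

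The denominator n is the number of patients given I-131. It is not known in advance. Two reference values are n = 4 (the vemurafenib pilot's 4 of 10, Section 3.2) and n = 10 (all of an MTD cohort of 6 + 4). One reclassified patient moves the proportion by 1/n.

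The table assumes half the patients are otherwise progression-free, with exact (Clopper-Pearson) 95% intervals: lower limit = Beta quantile(0.025; x, n − x + 1), upper limit = Beta quantile(0.975; x + 1, n − x).

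| n | Scored as event | Scored as progression-free | Shift (1/n) |
|---|---|---|---|
| 4 | 2/4 = 50% (6.8-93.2) | 3/4 = 75% (19.4-99.4) | 25 points |
| 6 | 3/6 = 50% (11.8-88.2) | 4/6 = 66.7% (22.3-95.7) | 16.7 points |
| 8 | 4/8 = 50% (15.7-84.3) | 5/8 = 62.5% (24.5-91.5) | 12.5 points |
| 10 | 5/10 = 50% (18.7-81.3) | 6/10 = 60% (26.2-87.8) | 10 points |

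The endpoint covers I-131 recipients at any dose level, and the planned sample is 6-32. If all 32 were treated, the shift would be 1/32 = 3.1 points.

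**The case against.** The case for leaving the text alone has real force.

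- **One growing lesion is normally not PD.** A reader might infer that any bone metastasis that grows and is irradiated is an erased progression. Section 12 does not support that, since growth of a single nontarget lesion does not normally qualify. Where progression does reflect the disease overall, irradiating one site would often leave PD visible elsewhere. This stands, and it makes the case uncommon. It does not make it impossible: Section 12 lets the treating physician's opinion prevail when only nontarget disease progresses, and other sites may have improved by 6 months.
- **Local control is not enough.** It is tempting to say that halting growth suffices. The comparison is with baseline, so a lesion that grew and then stopped can still read as progressed. It must regress. This stands.
- **New lesions do not pass through.** Section 12 defines nontarget lesions as those recorded at baseline and makes any new lesion PD. Radiation to a new lesion is outside the exemption.
- **ORR is not equally exposed.** Radiation to a nontarget lesion does not shrink target lesions. It can only remove a PD that would have blocked a response.
- **The exemption does not erase progression by itself.** The 6-month-versus-baseline rule does the erasing, with or without radiation. This is correct. But Section 14's reasons for that rule lose their force for an irradiated lesion, and the exemption is what keeps such a patient out of the event count.
- **A safeguard exists.** The physician's override may catch some cases. It turns on expected benefit, not on documented progression, and is discretionary in an unblinded single-arm study.
- **Radiation is recorded in the observation phase.** A reader might see an inconsistency with the exemption. There is none, because that recording serves a separate exploratory objective. It does mean cases could be identified.
- **Little depends on the result.** The endpoints are secondary, no decision rule in the available text uses them, and the intervals above overlap heavily. This limits the severity but does not justify a one-sided scoring rule that is easily corrected.

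**Conclusion.** The concern holds in a narrow form. With nontarget PD documented to the Section 12 standard, Section 14 still exempts palliative radiation to a nontarget lesion. Combined with the 6-month-versus-baseline reading, this allows the patient to be scored progression-free, and a responder if target lesions meet PR, unless the physician applies the override.

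The conclusion rests on the exemption's unconditional wording; the plan does not say expressly that radiation given for progression is exempt. It also requires enough regression that nontarget disease no longer reads as progressed against baseline. The size is 1/n per patient: 25 points at an assumed n = 4 and 10 points at n = 10. The expected number of such patients cannot be calculated, because the documents give no frequency of palliative radiation, and it is probably small. The documents do not support a claim of large or routine inflation of either endpoint. The correction is still worth making before analysis, because it is cheap and removes a case-by-case decision from a very small denominator.

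**What to change.** In Section 14, add one sentence: the exemption for palliative radiation to a nontarget lesion applies only when nontarget PD under Section 12 had not been documented on available assessments before the radiation; if it had, the patient is scored as a progression event and a nonresponder. At minimum, keep the present rule and report a sensitivity analysis that scores these patients that way.

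In the same edit, reconcile the first-progression definition of PFS in Section 12 with the 6-month-versus-baseline rule in Section 14. Otherwise unirradiated early progressors remain governed by two conflicting definitions. New lesions need no added rule. Declaring irradiated lesions not evaluable would add little, because the Section 12 table keeps PR or SD when nontarget disease is not evaluated.

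**Cost.** The rule uses assessments already available and requires no extra scan. Table 10-3 schedules post-I-131 imaging only at 3-4 and 6 months, so some progression before radiation will go undocumented, and those patients keep the exemption. The 6-month rates may be slightly less favourable. This is a scoring change only and does not affect whether a patient may receive radiation.

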15.0 RESEARCH PARTICIPANT REGISTRATION AND RANDOMIZATION PROCEDURES

15.1 Research Participant Registration

Confirm eligibility as defined in the section entitled Inclusion/Exclusion Criteria. Obtain informed consent, by following procedures defined in section entitled Informed Consent Procedures. During the registration process registering individuals will be required to complete a protocol specific Eligibility Checklist. The individual signing the Eligibility Checklist is confirming whether or not the participant is eligible to enroll in the study. Study staff are responsible for ensuring that all institutional requirements necessary to enroll a participant to the study have been completed. See related Clinical Research Policy and Procedure #401 (Protocol Participant Registration).

15.2 Randomization

Not applicable.

16.0 DATA MANAGEMENT ISSUES

A Clinical Research Coordinator (CRC) will be assigned to the study. The responsibilities of the CRC include project compliance, data collection, abstraction and entry, data reporting, regulatory monitoring, problem resolution and prioritization, and coordinating the activities of the protocol study team.

The data collected for this study will be entered into a secure database, Medidata Rave. Source documentation will be available to support the computerized patient record.

16.1 Quality Assurance

Weekly registration reports will be generated to monitor patient accruals and completeness of registration data. Routine data quality reports will be generated to assess missing data and inconsistencies. Accrual rates and extent and accuracy of evaluations and follow-up will be monitored periodically throughout the study period and potential problems will be brought to the attention of the study team for discussion and action.

16.2 Data and Safety Monitoring

The Data and Safety Monitoring Plan utilized for this study must align with the [MSK DSM Plan](#), where applicable.

The Data and Safety Monitoring (DSM) Plans at Memorial Sloan Kettering were approved by the National Cancer Institute in August 2018. The plans address the new policies set forth by the NCI in the document entitled "[Policy of the National Cancer Institute for Data and Safety Monitoring of Clinical Trials](#)."

There are several different mechanisms by which clinical studies are monitored for data, safety and quality. At a departmental/PI level there exists procedures for quality control by the research team(s). Institutional processes in place for quality assurance include protocol monitoring, compliance and data verification audits, staff education on clinical research QA and two institutional committees that are responsible for monitoring the activities of our clinical trials programs. The committees: Data and Safety Monitoring Committee (DSMC) for Phase I and II clinical trials, and the Data and Safety Monitoring Board (DSMB) for Phase III clinical trials, report to the Deputy Physician-in-Chief, Clinical Research.

During the protocol development and review process, each protocol will be assessed for its level of risk and degree of monitoring required.

The MSK DSMB monitors phase III trials and the DSMC monitors non-phase III trials. The DSMB/C have oversight over the following trials:

- MSK Investigator Initiated Trials (IITs; MSK as sponsor)
- External studies where MSK is the data coordinating center
- Low risk studies identified as requiring DSMB/C review

The DSMC will initiate review following the enrollment of the first participant by the end of the year one if no accruals and will continue for the study lifecycle until there are no participants under active therapy and the protocol has closed to accrual. The DSMB will initiate review once the protocol is open to accrual.

17.0 PROTECTION OF HUMAN SUBJECTS

Inclusion of Children in Research

This protocol/project does not include children, because the number of children with this disease is limited and because the majority of affected children are already accessed by a nationwide pediatric cancer research network. This statement is based on exclusion 4b of the NIH Policy and Guidelines on the Inclusion of Children as Participants in Research Involving Human Subjects.

Risks, Benefits, Toxicities/Side Effects

Potential risks to human subjects include drug-related toxicities, placement of IV catheters, phlebotomy, and possible psychological discomfort from the stresses associated with obtaining imaging studies (e.g., CT scan, PET scan). All efforts will be made to avoid any complication by completely reviewing patients' symptoms, providing appropriate management, and monitoring blood tests.

If an adverse medical event occurs, the patient will first contact the primary oncologist or the Principal Investigator. At nights and on weekends, there is an oncology physician on call at all times. Patients may either call or come directly to the urgent care center at Memorial Hospital (or to their local emergency room) to be seen. Patients suffering serious adverse reactions must be carefully followed and all follow-up information also recorded.

Alternatives/Options

Participation in this trial is voluntary. Depending on the specific details of the situation, patient options without being in a study might include:

- Other palliative chemotherapy off-study.
- Participation in a different clinical trial.
- Best supportive care.

Financial Costs/Burdens

The patient will be responsible for all costs related to treatment and complications of treatment. Costs to the patient (third-party insurer) will include hospitalizations, routine blood tests and diagnostic studies, office visits, baseline EKG, and doctor fees. Patients will not be charged the cost of analysis for the research correlates. Bayer will financially support the study, and Copanlisib will be supplied by Bayer. The patient will not be charged for the subsequent research analysis of these specimens. Vemurafenib is an NCCN compendium-approved medication. Serial 1-124 lesion dosimetry scans will be supported through R01 CA201250-03.

